7.3 Untoward Medical Events / Adverse Events

The definitions are the definitions in the current version of the ISO 14155. The categorization will adhere to the following table in ISO 14155;

Table 4 Untoward Medical Events / Adverse Events Categorization

ADVERSE EVENTS	Non-device related	Device-or-procedure related	
Non-serious	Adverse Event (AE) ^a (3.2)	Adverse Device Effect (ADE) (3.1)	
Serious	Serious Adverse Event (SAE) ^b (3.37)	Serious Adverse Device Effect (SADE) (3.36)	
		Anticipated	Unanticipated
		Anticipated Serious Adverse Device Effect (ASADE) (3.42, Note)	Unanticipated Serious Adverse Device Effect (USADE) (3.42)

References in parentheses refer to sections in the standard ISO 14155:2011

^a Includes all categories.

^b Includes all categories that are serious

Adverse events are any untoward medical occurrence, unintended disease or injury, or untoward clinical signs (including abnormal laboratory findings) in subjects, users or other persons, whether or not related to the investigational medical device.

The AE may be directly related to the use of an investigational medical device and are then called an adverse device effect (ADE). This includes events due to insufficient or incomplete instructions, use, implantation, or dysfunction of the tested product. Misuse and errors while using the product are also included in the ADE definition.

The following events are not considered untoward medical events / AEs:

- Medical interventions planned before study initiation given that the status of the participant has not worsened since signing the consent form or the intervention has had to be done at an earlier date.
- All conditions or diseases known at the time when the subject signs the informed consent form, are not considered untoward medical events / AEs. These will be registered in the medical history CRF page.

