3.5 Study Visits and Procedures

3.5.1 Day 0; Screening and Enrollment

Patients seeking treatment for symptoms relating to VVC may be informed about the study and, if agreeing to participate, sign the informed consent form (ICF). After enrollment, patients will have gynecological examinations performed, where the Investigator or an authorized designee will assess the presence of vulvovaginal signs (erythema, edema, or excoriation) and ask about symptoms (itching, burning, or irritation) and score each sign and symptom, as described in [Section 6.1](#).

Vaginal samples will be examined by microscope to reveal yeast forms (hyphae or pseudohyphae) or budding yeast. Two (2) vaginal secretion samples will also be collected by swab. One (1) of the samples will be cultured to verify presence of *Candida* and 1 sample will be used for sequencing analysis of the vaginal microbiome prior to treatment ([Section 7.2](#)). If the Investigator assesses that the patient has VVC, based on examination and the KOH test, the patient will receive the investigational product to be self-inserted vaginally at home on Day 0. Additional doses will also be dispensed to be administered by patients on Day(s) 2, 4, and 6. In addition, the Investigator will measure vaginal pH.

Procedures performed:

- Informed consent
- Eligibility criteria
- Pregnancy test (urinary)
- Recording of:
 - medical history,
 - concomitant medication, and
 - adverse events
- Gynecological examination by Investigator or authorized designee evaluating signs (erythema, edema, or excoriation) and symptoms (itching, burning, or irritation) of VVC according to the scoring scale
- Fungal KOH microscope assessment
- Vaginal swab for:
 - culture, and
 - sequencing
- Vaginal pH
- Treatment dispensing and self-administration by patients

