7.4 Serious Untoward Medical Events / Serious Adverse Events

An SAE is an AE that lead to serious deterioration in the health of the subject, that resulted in one or more of the below:

- death, or
- an immediately life-threatening illness or injury, or
- a permanent impairment of a body structure or a body function, or
- in-patient or prolonged hospitalization, or
- requires intervention to prevent life-threatening illness, or injury or permanent impairment to a body structure or a body function, or
- led to fetal distress, fetal death or a congenital abnormality or birth defect.

NOTE: Planned hospitalization for a pre-existing condition, or a procedure required by the current CIP, without serious deterioration in health, is not considered an SAE.

A serious adverse device effect (SADE) is an ADE that has resulted in any of the consequences characteristic of a SAE.

An unanticipated serious adverse device effect (USADE) is a SADE, which by its nature, incidence, severity, or outcome has not been identified in the current version of the risk analysis report

NOTE: Anticipated serious adverse device effect (ASADE) is an effect, which by its nature, incidence, severity, or outcome has been identified in the risk analysis report. The classification of an untoward medical event as USADE or ASADE will be done retrospectively. The event will initially be captured as an SAE.

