7.5.2 Relatedness

The Investigator's assessment of an AE's relationship to the device is part of the documentation process, but it is not a factor in determining what is or is not reported in the study. If there is any doubt as to whether a clinical observation is an AE, the event should be reported. The likely relationship of an AE to the device should be assessed by the Investigator according to the following definitions:

Not Related: Relationship to the device or procedures can be excluded when:

- the event is not a known^a side effect of the product category the device belongs to or of similar devices and procedures;
- the event has no temporal relationship with the use of the investigational device or the procedures;
- the serious event does not follow a known response pattern to the medical device (if the response pattern is previously known) and is biologically implausible;
- the discontinuation of medical device application or the reduction of the level of activation/exposure – when clinically feasible – and reintroduction of its use (or increase of the level of activation/exposure), do not impact on the serious event;
- the event involves a body-site or an organ not expected to be affected by the device or procedure;
- the serious event can be attributed to another cause (e.g. an underlying or concurrent illness/ clinical condition, an effect of another device, drug, treatment or other risk factors);
- the event does not depend on a false result given by the investigational device used for diagnosis^b, when applicable;
- harms to the subject are not clearly due to use error;
- In order to establish the non-relatedness, not all the criteria listed above might be met at the same time, depending on the type of device/procedures and the serious event.

Unlikely: The relationship with the use of the device seems not relevant and/or the event can be reasonably explained by another cause, but additional information may be obtained.

Possible: The relationship with the use of the investigational device is weak but cannot be ruled out completely. Alternative causes are also possible (e.g. an underlying or concurrent illness/ clinical condition or/and an effect of another device, drug or treatment). Cases were relatedness cannot be

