7.5.3 Outcome

The outcome or the result of the untoward medical event / AE for a participant will be rated by the Investigator as;

Resolved: Fully recovered spontaneously or after medical or surgical intervention, i.e., the status is the same as the pre-study status.

^a If an investigational device gives an incorrect diagnosis, the patient might, for example, receive an unnecessary treatment and incur all the risks that accompany that treatment, or might be incorrectly diagnosed with a serious disease. In other cases, the patient might not receive an effective treatment (thereby missing out on the benefits that treatment would confer), or might not be diagnosed with the correct disease or condition.

Resolved with sequelae:	As a result of the event the participant has remaining significant symptoms or loss of function as, but not limited to, blindness, deafness, or paralysis. All untoward medical events that the participant has not fully recovered from and has significant remaining symptoms or loss of function should be handled as serious untoward medical events / SAEs.
Ongoing:	The status of the participant has not improved and the symptoms are unchanged.
Death	
Unknown:	The status of the participant is unknown. This term is to be used only when no other term applies, e.g., when the participant is lost to follow-up.

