7.6 Capturing and Reporting of Untoward Medical Events / Adverse Events

Patients shall be asked about AEs at all visits (both site visits and telephone contacts). Questions for collecting AEs are specified in [Appendix 1, Section 4](#).

Adverse events can also be obtained from:

- Signs and symptoms from patient examinations,
- Laboratory values, or
- Spontaneous reports by subjects or their relatives.

All AEs and ADEs, will be captured in the section for AEs in the eCRF or in case of serious events in the section for SAEs, SADEs, or USADEs.

All events fulfilling the definition of untoward medical event will be captured and reported from the time when the participant signs the ICF and to the last visit in the study or until the participant has left the study. Untoward medical events may need follow-up after the last visit in the study before being rated as recovered or given a final status according to the definitions above.

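### Protocol 7.3 excludes conditions known at consent from adverse events with no limit for worsening, so worsening of entry symptoms can be missed or recorded inconsistently in the safety co-primary endpoint

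*Protocol*

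**What the plan says.** Protocol 7.3 defines an adverse event broadly and then lists two exclusions. The first, planned medical interventions, applies "given that the status of the participant has not worsened since signing the consent form". The second reads "All conditions or diseases known at the time when the subject signs the informed consent form, are not considered untoward medical events / AEs" and sends these conditions to the medical history page. It carries no limit for worsening.

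Two later sections lean towards reporting. Protocol 7.5.2 says: "If there is any doubt as to whether a clinical observation is an AE, the event should be reported". Protocol 7.6 names "Signs and symptoms from patient examinations" as one source of adverse events. The same section, however, ties capture to the definition: "All events fulfilling the definition of untoward medical event will be captured and reported from the time when the participant signs the ICF".

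Safety and tolerability is a co-primary endpoint and rests on reported treatment-emergent adverse events (protocol 2.1, SAP 3.1.1). Tolerability has no scale of its own and is read from the adverse events (protocol 7.10 and 9.2.3.1). SAP 7.10.2 treats an event as treatment-emergent if it starts after the first dose, and does not mention worsening. SAP 7.1.7 asks for a favourable outcome on both co-primary endpoints, with safety assessed descriptively.

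**The concern.** Patients enter because they seek care for vulvovaginal symptoms, and itching, burning and irritation are three of the six entry items. They are also what a local reaction to a vaginal product could look like: protocol 1.3.2 names vaginal itching or burning as the most common events with a comparable pessary. Read literally, the second exclusion removes these symptoms from adverse event reporting even if they get worse after dosing. Read together with 7.5.2 and 7.6, it does not. Neither document says which reading applies.

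This is the product's first clinical study. The adverse event table could omit local worsening, or include it for some patients and not for others. Recording is shared between the clinics, at visits, and a Clinical Trial Unit, by telephone, so different staff may settle the question differently.

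**Working it through.** The documents give no figure on this point to reproduce. The check compares passages and then shows what one patient is worth.

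**1. The two exclusions in 7.3.** One is conditional on no worsening; the next, in the same list, is not. A site can reasonably read the contrast as deliberate.

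**2. Does other text settle it?** Section 7.5.2 favours reporting where there is doubt, but a reader who takes 7.3 literally sees no doubt. Section 7.6 names examination findings as a source, but captures only events that meet the definition 7.3 has narrowed. The question put to patients about events (Appendix 1, Section 4) is an open one about health problems and does not prompt for worsening. The passages therefore conflict, and none expressly resolves the conflict.

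**3. What counts as known at consent?** Symptoms do, because they are why the patient attends. Signs are less clear. Protocol 3.5.1 has patients sign consent first, and then: "After enrollment, patients will have gynecological examinations performed". Erythema, edema or excoriation first seen at that examination was not necessarily known when the form was signed. The exclusion reaches entry symptoms most clearly.

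**4. Does the SAP settle it?** A worsening that the site reports as an event with onset after the first dose is already counted under SAP 7.10.2. The SAP is only unclear; the main gap is at the point of capture. The medical history tables (SAP 7.6) count patients with a condition and would not show that it worsened.

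**5. Do the item scores fill the gap?** Partly. Each item is summarised (SAP 7.9.2) and individual data are listed (SAP 7.1.1). But SAP 8.4 applies change from baseline only to the composite (CVVS) score, the symptom sum and vaginal pH, and SAP 8.6 and 8.7 count only reductions in sums. A rise in one item can be hidden in a falling sum. A constructed example, not a prediction:

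- Day 0: itching 3, erythema 2, burning 1, others 0. Composite 3 + 2 + 1 = 6; symptom sum 3 + 1 = 4.
- Day 7: burning 3, others 0. Composite 3; symptom sum 3.
- Changes: composite 3 − 6 = −3; symptom sum 3 − 4 = −1; burning 3 − 1 = +2.

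This patient counts as cured (composite 3 or below) and as reduced on both sums, while burning has gone from mild to severe.

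**6. Scale.** Assume all 24 planned patients are in the full analysis set and that k patients have a worsening that is not recorded and no other event. The reported incidence is then too low by k/24:

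- k = 1: 1/24 = 4.2 percentage points
- k = 2: 2/24 = 8.3 percentage points
- k = 3: 3/24 = 12.5 percentage points

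The values of k are assumptions. The documents give no basis for choosing among them.

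**The case against.** The strongest reply is that the second bullet covers only the baseline condition, which belongs in the medical history, and never says that later worsening is not an event. The general definition in 7.3 is broad, 7.5.2 tells the site to report when in doubt, and every contact includes a question about health problems. In substance this stands: the text is ambiguous, with a lean towards reporting. A reader might infer that the protocol removes all worsening from the safety data. The documents do not support that; they support only that it can be omitted or handled inconsistently.

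Two other passages might be cited for the reporting side. The note in 7.4 concerns planned hospitalization and serious events, and 7.5.3 only defines when an event is resolved. Neither says much about non-serious worsening.

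The reply also notes that the scores are collected and listed, so that with 24 patients a rise can be found by hand. That is true, and the data are not lost. A reader might go further and infer that no planned output counts such patients. That cannot be shown, because the mock tables are in the Data Display Plan, which was not available; the SAP text describes no such count.

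Finally, a reader might take the 10 patients with itching or burning in the comparable-pessary trial as a forecast for this one. The documents do not support this. That trial was in bacterial vaginosis, groups did not differ, and the share that was worsening of an entry symptom is not given.

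**Conclusion.** The concern holds as an unresolved conflict within the protocol, worth correcting because the change is cheap and the affected endpoint is co-primary. Worsening of entry itching, burning or irritation after the first dose can be left out of the reported adverse events, or recorded by some staff and not by others. Its frequency is unknown. Each affected patient with no other event is worth 4.2 percentage points of incidence, if all 24 planned patients are analysed. No hypothesis test is touched, since the safety endpoint has none, and the documents set no threshold for a favourable safety result.

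The conclusion rests on the wording of 7.3 as printed. That section adopts the definitions of an ISO standard that is not reproduced in full, so how the exclusion interacts with the standard could not be checked. The example of a falling sum shows only why the planned score outputs do not replace adverse event capture. It says nothing about how likely such a patient is.

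**What to change.** 1. **SAP tolerability output (main change).** Add the number and percentage of patients with an increase from Day 0 in each symptom on Days 4 and 7, and on Days 11 and 14 if treatment is prolonged. Do the same for each sign at the Day 7 examination and, if prolonged, the Day 14 examination. Label the table as unable to separate device irritation from lack of effect or disease progression. Leave out later contacts, where recurrence and rescue treatment confound the scores.
2. **Protocol 7.3.** Reconcile it with 7.5.2 and 7.6 by stating that conditions known at consent are not adverse events unless they worsen after consent.
3. **SAP 7.10.2.** State that treatment-emergent means starting or worsening after the first dose.

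The cost is one table from scores already collected and one clause in each document. The adverse event count may rise and include some disease progression. Protocol section 12 planned the last visit for February 2019, and the final SAP is dated 2020-01-14. If data collection had ended by then, the wording changes cannot alter what was captured, and only the table can have an effect.

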7.4 Serious Untoward Medical Events / Serious Adverse Events

An SAE is an AE that lead to serious deterioration in the health of the subject, that resulted in one or more of the below:

- death, or
- an immediately life-threatening illness or injury, or
- a permanent impairment of a body structure or a body function, or
- in-patient or prolonged hospitalization, or
- requires intervention to prevent life-threatening illness, or injury or permanent impairment to a body structure or a body function, or
- led to fetal distress, fetal death or a congenital abnormality or birth defect.

NOTE: Planned hospitalization for a pre-existing condition, or a procedure required by the current CIP, without serious deterioration in health, is not considered an SAE.

A serious adverse device effect (SADE) is an ADE that has resulted in any of the consequences characteristic of a SAE.

An unanticipated serious adverse device effect (USADE) is a SADE, which by its nature, incidence, severity, or outcome has not been identified in the current version of the risk analysis report

NOTE: Anticipated serious adverse device effect (ASADE) is an effect, which by its nature, incidence, severity, or outcome has been identified in the risk analysis report. The classification of an untoward medical event as USADE or ASADE will be done retrospectively. The event will initially be captured as an SAE.

7.5 Definitions of Adverse Event Ratings

7.5.1 Severity

Untoward medical events / AEs will be rated concerning their severity. The rating will be done by the Investigator. The rating used will be the following:

Mild: Transient symptoms, no interference with daily activities of the participant;

Moderate: Clear symptomatology that moderately affects the daily activities of the participant; or

Severe: Symptoms that clearly affects or hinders daily activities of the participant.

7.5.2 Relatedness

The Investigator's assessment of an AE's relationship to the device is part of the documentation process, but it is not a factor in determining what is or is not reported in the study. If there is any doubt as to whether a clinical observation is an AE, the event should be reported. The likely relationship of an AE to the device should be assessed by the Investigator according to the following definitions:

Not Related: Relationship to the device or procedures can be excluded when:

- the event is not a known^a side effect of the product category the device belongs to or of similar devices and procedures;
- the event has no temporal relationship with the use of the investigational device or the procedures;
- the serious event does not follow a known response pattern to the medical device (if the response pattern is previously known) and is biologically implausible;
- the discontinuation of medical device application or the reduction of the level of activation/exposure – when clinically feasible – and reintroduction of its use (or increase of the level of activation/exposure), do not impact on the serious event;
- the event involves a body-site or an organ not expected to be affected by the device or procedure;
- the serious event can be attributed to another cause (e.g. an underlying or concurrent illness/ clinical condition, an effect of another device, drug, treatment or other risk factors);
- the event does not depend on a false result given by the investigational device used for diagnosis^b, when applicable;
- harms to the subject are not clearly due to use error;
- In order to establish the non-relatedness, not all the criteria listed above might be met at the same time, depending on the type of device/procedures and the serious event.

Unlikely: The relationship with the use of the device seems not relevant and/or the event can be reasonably explained by another cause, but additional information may be obtained.

Possible: The relationship with the use of the investigational device is weak but cannot be ruled out completely. Alternative causes are also possible (e.g. an underlying or concurrent illness/ clinical condition or/and an effect of another device, drug or treatment). Cases were relatedness cannot be

^a When the event is not a known side effect of the product category the device belongs to or of similar devices and procedures, generally is considered "not related". Yet, the unexpected effect shall not be excluded from evaluation and reporting.

^b If an investigational device gives an incorrect diagnosis, the patient might, for example, receive an unnecessary treatment and incur all the risks that accompany that treatment, or might be incorrectly diagnosed with a serious disease. In other cases, the patient might not receive an effective treatment (thereby missing out on the benefits that treatment would confer), or might not be diagnosed with the correct disease or condition.

assessed or no information has been obtained should also be classified as possible.

Probable: The relationship with the use of the investigational device seems relevant and/or the event cannot reasonably explained by another cause, but additional information may be obtained.

Causal Relationship: The serious event is associated with the investigational device or with procedures beyond reasonable doubt when:

- the event is a known side effect of the product category the device belongs to or of similar devices and procedures;
- the event has a temporal relationship with investigational device use/application or procedures;
- the event involves a body-site or organ that
 - the investigational device or procedures are applied to;
 - the investigational device or procedures have an effect on;
- the serious event follows a known response pattern to the medical device (if the response pattern is previously known);
- the discontinuation of medical device application (or reduction of the level of activation/exposure) and reintroduction of its use (or increase of the level of activation/exposure), impact on the serious event (when clinically feasible);
- other possible causes (e.g. an underlying or concurrent illness/ clinical condition or/and an effect of another device, drug or treatment) have been adequately ruled out;
- harm to the subject is due to error in use;
- the event depends on a false result given by the investigational device used for diagnosis^a, when applicable;
- In order to establish the relatedness, not all the criteria listed above might be met at the same time, depending on the type of device/procedures and the serious event.

